1.4 Methodology

A population-based CRT with associated mixed methods sub-studies. The intervention will be delivered through CBDAs, trained by PSI to provide HIVST in their rural villages. 20 ART Clinics and their catchment populations will be randomised to either HIVST or standard of care (SOC) arms. The ~200 CBDAs in the HIVST arm will be trained to provide HIVST (OraQuick ADVANCE HIV I/II test kits, packaged for self-use) along with reproductive health products. CBDAs will provide brief pre-test information and a self-referral form with all kits to facilitated linkage into HIV care and prevention services. Posttest advice will be provided for all who confide positive HIVST results.

Outcomes will be captured at 12 months through:

- 1. Household level surveys (~5,000 adults) at baseline and after 12 months of intervention .These will include questions on recent HIV testing through any modality (**Primary Outcome**).
- 2. ART clinic records to investigate whether or not population-level demand for ART has increased (**Secondary Outcome**).

A second stage randomisation of HIVST CBDAs will further explore the role of homebased HIV care assessment for encouraging disclose of positive HIVST results and ART initiation. This is an implementation research study, and no biological specimens will be required for research other than for pilot accuracy evaluation.

The study will be preceded by pilot studies to test the ability to interpret pictorial instructions and accurately use and interpret HIVST kits (packaged with instructions in Chichewa). The trial will be accompanied by economic evaluations. Interviews with key informants will be used to explore the policy and regulatory landscape for HIVST. Tools developed for the main study will be evaluated in other community volunteer cadres, notably voluntary medical male circumcision mobilisers.

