4.1 Main trial

The main study will be a cluster-randomised trial in up to 5 high HIV prevalence districts (provisionally Blantyre, Machinga, Mwanza, Neno and Thyolo) that already have community-based reproductive health services provided by PSI under funding provided by the German Technical Cooperation Agency (GTZ). This programme supports volunteers to socially-market reproductive and child health products in villages, with products stored and managed by collaborating primary care clinics.

Figure 4. Schematic illustration of Standard of Care and HIVST intervention clusters intervention provided by village-based CBDAs.

Unit of randomisation is the Primary Care + ART Clinic (black cross) and surrounding catchment area villages (large circles with feed-in arrows) to clinic. CBDAs in the HIVST Arm villages will be trained to provide HIVST services as well as reproductive health services (**small solid circles**). CBDAs in the SOC Arm villages will remain with reproductive health services only (**small open circles**). Two separate units of evaluation will be pre-defined before randomisation: one or two evaluation villages that will have baseline-final household surveys, and a wider catchment area including all villages with CBDA activities.

The unit of randomisation will be the **primary care clinic**. The **unit of evaluation** will be defined by **clinic records of adult ART initiations** from villages within the wider CBDA catchment area, and through household survey of **1 to 2 evaluation villages** contained within the catchment population (Figure 5).

The trial will compare **population-level uptake of ART** (as defined by ART clinic records of new initiators listing study villages as their home address) and **coverage of recent HIV testing** (as defined by household surveys) between two arms:

- 1. **Intervention arm**: Addition of HIVST kits, with brief training and IEC material, to the products carried by PSI-supported reproductive health CBDAs, or
- 2. **SOC arm**: CBDAs will continue to offer reproductive health services, but without the addition of HIVST kits

Figure 5. Trial timelines

In a **second-stage randomisation arm**, villages included in the HIVST intervention will be further randomised to

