4.3 Primary and secondary outcomes

4.3.1 Primary Outcome for main HIVST versus SOC CBDA intervention

The primary outcome is: Comparison between randomisation arms in coverage of recent (within the last 12 months) HIV testing among adult (16 years and above) village residents 12 months after the initiation of the intervention.

A related pre-specified analysis is to compare between randomisation arms the coverage of ever (lifetime) HIV testing among adult (16 years and above) village residents.

These analyses will be based on household surveys carried out in the pre-defined evaluation villages in each randomisation arm.

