5.2.2 Baseline household surveys

All households in the evaluation villages will be visited for enumeration and invited to participate in the baseline household survey (PS401A). Village boundaries will be defined by obtained GPS coordinates.

An appointment will be made to visit the head of household or authorised individual to explain the study. All adults and older adolescents will be asked for verbal consent to participate, with verbal consent from guardians required in the case of adolescents.

As part of the baseline household survey, a household-level questionnaire of household size, age and gender composition, and socioeconomic indicators will be administered. Each adult household member will then be asked for verbal consent to participate in a brief individual questionnaire on demographic characteristics and experience with HIV testing and care.

A random selection of participants will then also be asked for written consent to complete an extended individual questionnaire on sexual behaviour, stigma, and health service utilisation, including costs. A discrete choice module will investigate user preferences for HIV delivery and linkage to care.

One in 4 household survey participants will be randomly allocated to a longer questionnaire (PS401B/PS402A), includes an approach to establishing user preferences by asking participants to make a series of trade-off choices (discrete choice experiment: DCE). Written or witnessed informed consent (or assent with guardian consent in the case of adolescents) will be obtained beforehand. Selection will be determined based on a random number generated by the electronic survey device at the time of the household survey (Choko, et al. 2015).

A post-intervention survey will be conducted with the same evaluation villages 12 months after the start of HIVST services. The post-intervention survey will consist of the household and brief individual questionnaires as well as an additional section on self-testing.

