5.8.1 Description of the HIVST and SOC arms in the baseline survey

The characteristics of participants recruited into the baseline survey will be described by arm (HIVST and SOC). Cluster-level factors will be summarised at baseline using the mean, median and range, by intervention arm, based on data from the facility assessment, conducted at baseline.

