5.8.5 Methods

All statistical analyses will be based on methods used for CRTs with a small number of clusters (Campbell, et al. 2012). The analysis for the first randomisation is based on a total of 20 clusters.

Summary measures

For binary outcomes the overall risk, combining data across clusters, and means of clusterlevel risk will be reported by intervention arm. For quantitative outcomes, the overall mean and cluster-level means will be reported by intervention arm.

Unadjusted analysis

The analysis will give each cluster equal weight. The overall risk/mean for each cluster will be calculated.

A log transformation (where necessary) will be applied to the risk/rate/mean for each cluster. For binary outcomes where there are clusters with no events, one event will be added to all clusters so that the log transformation can be conducted. The mean and standard deviation of these log risks/rates/means will be used to obtain the geometric mean (GM) and associated 95% CI for each arm of the study.

The risk/mean ratio, 95% confidence interval and p-value is estimated using a t test and the log risks/rates/means by arm, based on 18 degrees of freedom.

Adjusted analysis

Factors for adjustment will be determined as stated above.

Depending on the outcome to be analysed, logistic/linear regression will be used to adjust for confounders at the individual level and cluster level, adopting a two-stage approach.

The regression model will include terms for the individual level adjustment factors, but not study arm. For each cluster the fitted model will be used to obtain the ratio of observed to expected (O/E) events, and a log transformation will be applied to this ratio, where appropriate. A t test of the log (O/E) by arm will be used to estimate the risk ratio, 95% CI and p-value. If adjustment for cluster level factors is considered necessary, this will be conducted at the second stage using linear regression of the log (O/E) on arm and cluster level factors, with appropriate adjustment for the degrees of freedom.

Stratified (subgroup) analyses

Stratified analyses (sub-group) for the primary outcome will be pre-specified before the end of data collection,

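### Baseline testing coverage is collected in every cluster before randomisation, but no outcome analysis commits to adjusting for it

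*Protocol*

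**What the plan says.** **Data collected.** Section 1.4 plans "Household level surveys (~5,000 adults) at baseline and after 12 months of intervention", with recent testing as the primary outcome. Section 4.1 fixes, before randomisation, "one or two evaluation villages that will have baseline-final household surveys". Under 5.2.2 each consenting adult at baseline answers a "brief individual questionnaire on demographic characteristics and experience with HIV testing and care", and the post-intervention survey returns to the same villages. Section 5.3 places the constrained allocation after baseline enumeration.

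**Outcomes.** Section 4.3.1 makes testing in the last 12 months the primary outcome and adds: "A related pre-specified analysis is to compare between randomisation arms the coverage of ever (lifetime) HIV testing".

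**Analysis.** In 5.8.5 the unadjusted comparison is a t test on log cluster risks with 18 degrees of freedom. The adjusted analysis takes its factors from what was said earlier in the section. It handles individual-level factors at stage one, then states: "If adjustment for cluster level factors is considered necessary, this will be conducted at the second stage", by linear regression of log(O/E) on arm and cluster factors.

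**Choice of factors.** The general rule is in 5.8.2: variables substantially imbalanced between arms in the follow-up survey. Section 5.8.1 uses the baseline survey for description and takes its cluster-level factors from the facility assessment. For the ART outcome only, 5.8.4 names a pre-intervention value as a candidate covariate, again subject to imbalance.

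**The concern.** Each of the 20 clusters will have its own pre-randomisation value of the primary outcome, and probably of ever testing. Under the protocol's assumptions most of the error in the arm comparison is variation between clusters, and a baseline value of the same outcome is a natural covariate for absorbing it. The adjustment rule serves a different purpose. It is triggered by imbalance, judged on follow-up characteristics and left to discretion, so it guards against confounding and does not aim at precision. It also leaves the choice of covariates open until follow-up data are in hand.

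What is at stake is the width of the interval for recent testing and, more so, for ever testing. Figure 11 asks for 10.44 clusters per arm at 50% vs 70% and 16.33 at 50% vs 65%, against 10 planned. Lifetime testing cannot be undone, so village differences in ever testing should tend to persist, apart from migration and reporting.

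**Working it through.** **Inputs from section 7.2:** m = 250 adults per cluster, k = 0.25, 10 clusters per arm. Recent testing is assumed at 25% to 40% with a relative increase of 45% to 60%; ever testing at 42% to 60% with an increase of 30% to 45%. **Assumed, not in the protocol:** rho, the true correlation between a cluster's baseline and 12-month coverage.

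**1. The plan's own figure.** c = 1 + (z_0.975 + z_0.80)² × [p0(1−p0)/m + p1(1−p1)/m + k²(p0² + p1²)] / (p1−p0)². For 30% vs 45%, the bracket is 0.00084 + 0.00099 + 0.01828 = 0.02011, and (1.960 + 0.842)² = 7.849. So c = 1 + 7.849 × 0.02011/0.0225 = 8.02, as printed in Figure 10. All 24 rows of Figures 10 and 11 reproduce.

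**2. Unadjusted power with 10 clusters per arm.** Using the same variance V (the bracket above) and a noncentral t with 18 df, the noncentrality is (p1−p0)/√(V/10). For 30% vs 45% this is 0.15/√0.002011 = 3.34, giving 88.5%.
- Recent testing from 30%: 83% at +45%, 88.5% at +50%, 95% at +60%.
- Ever testing from 50%: 57% at +30%, 78% at +40%, 85% at +45%.

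**3. How much of the error is between clusters.** On the log scale, the variance of a cluster's observed coverage is about k² + (1−p)/(mp). At 30% this is 0.0625 + 0.7/75 = 0.0718, so the between-cluster share is 0.0625/0.0718 = 87%. The share is 84% at 25%, 94% at 50% and 96% at 60%. Baseline cluster coverage is therefore measured with little sampling noise.

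**4. Effect on interval width.** Adjusted to unadjusted width is about (t_17/t_18) × √[(1−r²)(1 + 1/16)], where r is the observed within-arm correlation and 1/16 allows for chance baseline imbalance. At r = 0 this is (2.110/2.101) × √1.0625 = 1.035. Sampling noise makes r smaller than rho: taking the baseline share for both surveys, r ≈ 0.87 rho at 30% and 0.94 rho at 50%. For recent testing at rho = 0.5, r = 0.435 and the ratio is 1.035 × √(1−0.189) = 0.932.

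**5. Simulated power.** The simulation used 10 clusters per arm, log-normal cluster effects with k = 0.25 correlated rho between surveys, two independent binomial samples of 250 and no randomisation constraint. The analysis was either the 18-df t test on log risks or regression on arm and log baseline coverage (17 df).

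| rho | Recent (30%, RR 1.45): width ratio | Recent: power | Ever (50%, RR 1.30): width ratio | Ever: power |
|---|---|---|---|---|
| unadjusted | 1 | 85% | 1 | 59% |
| 0 | 1.035 | 83% | 1.035 | 56% |
| 0.3 | 0.999 | 84% | 0.993 | 60% |
| 0.5 | 0.932 | 90% | 0.914 | 68% |
| 0.7 | 0.821 | 96% | 0.780 | 80% |

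Width ratios come from step 4 and powers from the simulation, which is good to about one percentage point. Unadjusted power is about two points above step 2 because the planned test works on logs, while the sample-size formula works on proportions. Type I error stayed near 5% for both analyses.

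**The case against.** **The choice of covariates belongs in the SAP, which is not shown.** This stands in part. Section 5.8.5 already contains the regression that is needed, and its optional clause would admit baseline coverage. A reader might infer that the protocol rules out using the baseline data; it does not. But the protocol goes further than leaving the matter open: it sets a rule based on imbalance, follow-up data and discretion, and that rule works against a routine precision adjustment.

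**The primary analysis is adequate without it.** This stands. A reader might infer that the t test is wrong or the trial underpowered. The test is valid, and step 2 shows 83% to 95% power across the predicted effects from 30%. Nor is ever testing weak for every realistic effect: power is 85% at the top of the predicted range, and the shortfall lies towards the lower end.

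**The gain is not assured.** This stands. Rho appears nowhere in the protocol. The two 12-month recall windows for recent testing largely do not overlap, and testing in the HIVST arm will also depend on how actively each CBDA distributes kits, so a high rho is not established for the primary outcome. A definite loss of precision cannot be claimed.

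**Two further limits stand.** Baseline ever testing is inferred from the description of the questionnaire. The constraint variables for the randomisation are not named, so their effect on the gain is unknown.

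**Conclusion.** The point holds as a missed commitment. The protocol collects the baseline value of its primary outcome in the clusters where that outcome will be measured, before allocation, and no outcome analysis undertakes to adjust for it. Adjustment offers a likely, nearly free gain in precision: none of substance at rho of about 0.3, intervals about 7% to 9% narrower at 0.5, and about 18% to 22% narrower at 0.7. In power, that is about 5 and 11 points for recent testing at RR 1.45, and about 9 and 21 points for ever testing at RR 1.30, at rho 0.5 and 0.7 respectively. The case is strongest for ever testing, where planned power is lowest and persistence between surveys is most plausible. All these sizes rest on the assumed rho, the protocol's k = 0.25 and 250 adults per cluster, and unconstrained allocation.

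**What to change.** In 5.8.5, and in the SAP to match, state that the main analysis of recent testing is a second-stage linear regression of the 12-month cluster log risk (or log O/E) on arm and the cluster's log baseline coverage of recent testing. It uses 20 − 3 = 17 degrees of freedom and applies whatever imbalance is seen. Specify the same for ever testing with baseline ever-tested coverage, after confirming that the baseline questionnaire records it. Keep the unadjusted 18-df t test as a supportive analysis.

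The cost is a sentence or two of text, with no new data if baseline ever testing is recorded. Statistically it costs one degree of freedom: if baseline and follow-up coverage proved unrelated, the interval would be about 3% wider, or about 3 points of power.

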6.1. HIVST

HIV testing and counselling including HIVST is well established, and known to have a high level of safety and favourable risk: benefit ratio. However, harmful reactions can occur. For the purposes of this trial, we will focus on capture of the following **Serious Adverse Events.**

- Death or hospitalisation due to self-inflicted injuries within 30 days of a positive HIVST results
- Death or hospitalisation resulting from violent assault by others (intimate partner violence, assault by family members, assault by community members) within 30 days of a positive HIVST result

Deaths and hospitalisations will be captured through the Social Harms System established in each cluster. The PSI Supervisor will interview the client and relatives to establish relatedness where possible.

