- 1. Arm 1A: HIVST plus optional home assessment for HIV care. CBDAs will offer all clients willing to confide their preliminary positive result the option of having their confirmatory testing and initial HIV care assessment (registration card and the first 2 weeks of cotrimoxazole and ART, if eligible) at home, or
- 2. Arm 1B: HIVST only: CBDAs will offer advice and encouragement to all clients to confide a preliminary positive result, in order to allow the OraQuick test to be repeated by the CBDA who will then provide a written referral slip to the nearest ART clinic.

Figure 6. Summary of HIVST CRT arms and second stage randomisation

Home-based assessment from HIV care following HIVST was shown to be effective in urban Blantyre (MacPherson, et al. 2012).

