Once a client requests home assessment, the CBDA will be responsible for arranging a clinical (ART trained nurse) visit to the participant's home or designated meeting point within 3 days to carry out confirmatory HIV testing, WHO staging, CD4 cell count (Alere PIMA CD4), and TB screening. They will also provide 2 weeks of Co-trimoxazole and ART if the participant meets eligibility requirements. Participants will then be provided with a completed ART registration card and follow-up appointment at the ART clinic.

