5.6 Outcome evaluation

5.6.1 Data Capture

Four data collection channels will be employed for the impact evaluation:

- 1. Pre- and post-intervention household surveys
- 2. CBDA registers and forms
- 3. ART clinic registers and forms, and
- 4. Harms monitoring records.

Data will be collected using tablet computers and paper-based forms.

CBDA logbooks and forms

Process data on HIVST distribution by CBDAs will be captured using HIVST logbooks (date, name, village and number of test-kits taken), returned kits, self-completed questionnaires (SCQ), and self-referral cards for ART clinics.

The SCQ will include questions about the self-read HIVST result, satisfaction, coercion, and HIV testing and ART history. The returned kits will be collected and read against the SCQ by field supervisors before disposal. This will allow the study team to conduct confirmatory readings of HIVST results and provide an ongoing measure of accuracy. CBDAs will also use registers to track the age, sex and HIV and ART history of participants and the nature of support received for HIVST.

ART registers and forms

To monitor the number of referrals, HIV diagnoses and ART initiations, the study will extract routine facility records and, if applicable, self-referral cards from ART clinics serving the evaluation villages.

Harms monitoring records

Identified community leaders will provide weekly reports of deaths and any known episodes of domestic violence. CBDAs will then investigate any possible links to HIVST.

Data capture forms and questionnaires are shown in the Appendices

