5.6.4 Outcome evaluation

For the comparison of **coverage of recent** / **ever HIV testing**, outcomes will be evaluated through household surveys as detailed above.

For evaluation of **ART initiations within study area villages**, maps showing study area boundaries and names of participating villages will be produced and displayed in HCT and ART clinics. ART register completion will be adjusted in collaboration with MoH to allow previous HIVST / home-initiation episodes to be documented in the "Comments" column.

Clinic staff will be asked to ensure that all clients are asked directly if they are attending following HIVST results and that the village of residence is clearly recorded in the ART register. The self-referral cards, which are presented by the participants to the clinic, will contain spaces for ART clinic staff to log confirmatory results, the national ART number for clients entering HIV care, and any other relevant referrals (e.g., VMMC).

PSI CBDA supervisors will extract these data on a monthly basis from each of the 20 ART clinics included in the study. Retrospective data extraction will also be used to provide an indication of pre-intervention ART initiations from the 20 study clinics.

In **Home-Initiation villages**, where participants have the option of requesting home initiation of care, PSI CBDA supervisors will fill out HIV care registration cards and maintain a logbook allowing cross-reference by ART number with the local ART clinic. Total numbers of clients confiding positive HIVST results will be recorded by all CBDAs in post-test logbook recording disclosure and other referral events without name.

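### The two SAE types named in section 6.1 do not cover home-started ART and co-trimoxazole in Arm 1A, and no text gives a medical or drug-related death or admission after a home start the SAE reporting steps.

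*Protocol*

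**What the plan says.** **Treatment.** Sections 4.1 and 4.3.3 randomise HIVST villages to self-testing alone or to self-testing with optional home assessment and start of care. Arm 1A clients who confide a positive result may have confirmatory testing and the "initial HIV care assessment (registration card and the first 2 weeks of cotrimoxazole and ART, if eligible) at home". Section 5.4.1 says of the visiting clinical staff: "They will also provide 2 weeks of Co-trimoxazole and ART if the participant meets eligibility requirements".

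**SAE definition.** Section 6.1, headed HIVST, begins "we will focus on capture of the following" and lists two items. The first is "Death or hospitalisation due to self-inflicted injuries within 30 days of a positive HIVST results". The second is death or hospitalisation from assault by a partner, family or community members, again within 30 days of a positive result.

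**Capture.** Section 6.1 continues: "Deaths and hospitalisations will be captured through the Social Harms System established in each cluster". The PSI Supervisor then interviews the client and relatives about relatedness. Section 5.6.1 adds: "Identified community leaders will provide weekly reports of deaths and any known episodes of domestic violence", and "CBDAs will then investigate any possible links to HIVST". Section 10.1 adds a hotline for adverse events.

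**Reporting.** Under 6.2, SAEs go at once to the PI or MLW Coordinator, and full SAE listings go to the ethics boards every 12 months. All remaining adverse events are logged and put in follow-up reports described only as regular. Section 6.3 requires an SAE form and a PI assessment of seriousness and relatedness.

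**The concern.** Arm 1A gives drugs outside a clinic as part of a randomised component, but the SAE section is written around the social harms of self-testing. A severe reaction to ART or co-trimoxazole, or a death from a condition missed at the home assessment, is a risk of the home start and not of the test kit. Staff deciding whether to report such an event immediately find no text telling them to. It could be logged without prompt PI review and be absent from the SAE listing that the ethics boards see.

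The evidence cited in 6.2 for the reporting approach, no suicides in 27,000 HIVST episodes, concerns self-testing and says nothing about drugs started at home. This is a matter of patient-safety reporting. It does not touch the primary or secondary outcomes.

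**Working it through.** The protocol states no figure to reproduce. The check sets the safety text beside the treatment text.

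1. **Does the trial itself start drugs at home?** Yes, by sections 4.1 and 5.4.1. Section 4.3.3 gives the supply as 14 days.

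2. **Do the named SAE types cover a medical or drug-related cause?** Type 1 requires self-injury and type 2 requires assault. Count: 0 of 2.

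3. **Which steps are stated for SAEs and not for other adverse events?**
   - immediate report to the PI or MLW Coordinator (6.2)
   - 12-monthly listing to the ethics boards (6.2)
   - SAE form (6.3)
   - PI review of seriousness and relatedness (6.3)

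   Count: 4.

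4. **Trace one event.** Suppose an Arm 1A client is admitted with a severe drug reaction during the two-week home supply.
   - *Capture:* the admission falls within what the Social Harms System collects, and the supervisor's interview has no stated limit on cause.
   - *Classification:* it is neither self-injury nor assault. On the natural reading it joins the remaining adverse events in 6.2.
   - *Reporting:* it is logged and put in follow-up reports with no stated interval. None of the 4 steps is stated for it.

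5. **Trace a death after a home start.** Community leaders report it within the weekly cycle. The next step in 5.6.1 is "CBDAs will then investigate any possible links to HIVST". Home care follows from a shared positive self-test, so a CBDA might count a treatment death as linked, but the text does not say so.

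6. **Can such events be identified with existing records?** Section 5.6.4 says that "PSI CBDA supervisors will fill out HIV care registration cards and maintain a logbook allowing cross-reference by ART number with the local ART clinic". Deaths and admissions from the Social Harms System can be set against that logbook.

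7. **Window for an added class.** The two existing types use 30 days. Counted from the home start, 30 − 14 = 16 days remain after the home supply ends.

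**The case against.** The strongest reply is that 6.1 does not close the SAE class. Its lead-in, "we will focus on capture of the following", sets a priority and is not a definition. Section 6.2 speaks of SAEs that are expected, which implies that some are not. Section 6.3 has the PI judge seriousness, a step with little purpose if every SAE is already a death or hospitalisation. The capture sentence, "Deaths and hospitalisations will be captured through the Social Harms System established in each cluster", names no cause. This stands: a reader might infer that the protocol excludes drug-related events from the SAEs, and the wording does not go that far. It does not include them either, and no route is stated for them.

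A reader might also infer that such events go unseen or unreported. The documents do not support that. There are weekly death reports, a hotline, a log and follow-up reports. Section 6.2 describes 6-monthly progress reports covering safety, and 5.3 mentions a Data Safety Monitoring Board. Neither is given a stated role for home-start drug events.

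Clinical safeguards also exist. Section 5.4.1 specifies an ART-trained nurse, confirmatory testing, WHO staging, a CD4 count, TB screening, eligibility requirements and a clinic follow-up appointment. The drugs are ordinary HIV care. This lowers the risk but does not say how an event is reported. Routine clinic drug-safety reporting, or the SOPs mentioned in 5.6.3, may supply a route, but the protocol states none.

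**Conclusion.** The point holds as a gap in stated reporting. Section 6.1 names only self-injury and assault after a positive self-test, and no text gives a medical or drug-related death or admission after a home start any of the four SAE steps. The link check in 5.6.1 names HIVST only.

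The size is 0 of 2 named types and 4 steps. These are counts of wording and do not measure harm. The protocol gives neither a number of home starts nor an interval for the follow-up reports, so no event rate or delay can be estimated.

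The conclusion rests on the natural reading of 6.1 and 6.2; under the wider reading the same change is a clarification. It also assumes that no document outside the protocol already sets a route. SAE definition and expedited reporting are protocol content, so this is not a matter left to an SAP. The change should be made; confidence is medium because the SAE wording is open.

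**What to change.** - **Section 6.1:** add a third SAE class, death or hospitalisation from any cause within 30 days of home-started ART or co-trimoxazole. Find these events through the Social Harms System and the home-initiation logbook, and send them by the existing immediate route.
- **Sections 6.1 and 6.2:** report any suspected serious drug reaction that comes to staff notice (hotline, CBDA or ART-clinic follow-up visit) by the same route. Do not claim systematic capture of reactions without admission, because neither the Social Harms System nor the logbook is described as recording them.
- **Sections 6.1, 6.3 and 5.6.1:** state that the relatedness review and the link check cover home-started treatment as well as HIVST.

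**Cost.** These are wording changes. The deaths and admissions need no new capture system, assuming the logbook holds the date of the home start, which 5.6.4 does not say. There are three downsides:
- Some additional immediate reports will arrive, most of them unrelated to treatment.
- Matching events to the logbook needs care over confidentiality.
- The class applies only to home starts, so its counts are not comparable between Arms 1A and 1B and should not be used as a between-arm comparison.
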